**List of tables**

Table 1: Vaccine Formulation (0.5 mL Dose) .....	10
Table 2: Guidelines for Pregnant Subjects: Managing Study Visits and Study Vaccinations .....	19
Table 3: Evaluating Adverse Events .....	26
Table 4: Acceptable Day ranges for Vaccination Visits .....	30
Table 5: Acceptable Day Ranges for Collection of Serum Samples .....	31
Table 6: Analysis Strategy for Safety Parameters .....	33
Table 7: Investigational medicinal product .....	36

## RATIONALE for Amendment 1

In the HIV group we anticipated a sample size of 140 patients which was deemed feasible since 471 HIV patients between 18 and 46 years of age were followed in the university hospitals of Leuven. However, at the start of study only a list of 366 eligible patients was available, of whom 69 have been enrolled in the study to date, 8 have discontinued treatment at the hospital, 105 patients will be approached in the near future and 198 had to be excluded during screening. The main reasons for exclusion were a history of condylomata (n = 56), a history of low grade vaginal, vulvar, cervix or anal neoplasia (n = 19), not deemed to be eligible by the treating physician, and no interest or no time. Based on the current response and eligibility rates, we estimate that in total about 70 patients can be included according to the current study protocol.

Based on this finding, literature on HPV vaccination in HIV patients was looked into again and a recalculation of the initial sample size was done based on the following findings:

- Prior to the start of the study, a sample size calculation was based on an expected seroconversion rate of 85%-91% for HPV type 18 (most stringent seroconversion rate) and allows to estimate the proportion of seroconverted patients with a margin of error (precision) of  $\pm 5.9\%$  to  $\pm 4.7\%$  (1). The expected seroconversion rates for types 6, 11, and 16 are higher ( $> 95\%$ ), and thus with a smaller margin of error (less than  $\pm 3.6\%$ ).
- The expected seroconversion rates that were used for the sample size calculation were retrieved from published data of patients with a CD4-count of 200-350 cells/mm^2. However, 92% of the patients that are currently included have a CD4-count of  $> 350$  cells/mm^2, which makes seroconversion rates in patients with more than 350 CD4+ cells/mm^2 more applicable (1). Published seroconversion rates in these patients are 95%-99% for HPV types 6, 11 and 16 and 90% for HPV-18.
- This sample size calculation does not take in to account that patients might be seropositive to certain HPV-types at baseline and that their data will be excluded for the analysis of the seroconversion outcome of the corresponding HPV-type. Seroprevalence to different HPV-types in previous studies on the safety and immunogenicity of the quadrivalent HPV-vaccine in HIV patients ranged from 13% to 45% for the different vaccine HPV-types (1-3).
- In order to maximize the number of eligible subjects, we amend the protocol to also **include patients with a history of abnormal PAP-smears without treatment or genital warts**. We believe that this allows us to reach a total sample size of at least 100 HIV-patients. Patients who are seropositive for a given HPV-type at baseline will

still be excluded for the analysis of seroconversion of that particular type but will still be useful for the analysis of the other HPV-types. Knowing that in HIV-patients the expected seroconversion rate of HPV-18 is relatively lower than the seroconversion rates of HPV types 6, 11 and 16, maximizing the number of eligible subjects for the analysis of this type is especially beneficial in order to obtain a reasonable margin of error. Enrolling patients with history of genital warts, who are most likely seropositive to HPV types 6 or 11, still allows us to increase the number of HPV-18 seronegative patients. In addition, clinical presentation of HPV infection does not necessarily implicate seropositivity to HPV.

- **With a total sample size of n=100, a majority of whom will have no history of HPV-lesions, we expect to be able to use the data of at least 80 patients for the analysis seroconversion of each HPV type under study. Seroconversion rates of 95-99% for HPV types 6, 11 and 16 can then be estimated with a margin of error of  $\pm 4.8\%$  -  $2.2\%$ , and the anticipated seroconversion rate of 90% for HPV type 18 with a margin of error of  $\pm 6.6\%$ .**

**The amendment to the study protocol therefore includes an adaptation of the study protocol which consists of a reduction of the planned sample size (from 140 to 100), and a wider recruitment in order to fulfil the aims of the study.**

## ABBREVIATIONS AND DEFINITIONS

9vHPV	9-valent (6/11/16/18/31/33/45/52/58) human papillomavirus vaccine
AE	adverse event
ANSS	all type-specific naïve subjects with serology
cLIA	competitive Luminex® immunoassay
CRF	case report form
CSP	clinical study protocol
CSR	clinical study report
EDC	electronic data capture
EU	European Union
GMT	geometric mean titre
HIV	human immunodeficiency virus
HPV	human papillomavirus
ICF	informed consent form
IEC	independent ethics committee
IMP	investigational medicinal product
IRT	Interactive response technology
mAbs	monoclonal antibodies
mMU/mL	milli merck units per millilitre
MSD	Merck Sharp & Dohme Corp., a subsidiary of Merck&Co
PPI	per protocol immunogenicity
qHPV	quadrivalent human papillomavirus vaccine
SAE	serious adverse event
SOT	solid organ transplantation
VLP	virus-like particles

## **1. PROTOCOL SYNOPSIS**

### **1.1. Title**

An Open-label phase III study to investigate the immunogenicity and tolerability of a nine-valent human papillomavirus (HPV) vaccine (Gardasil®9) in solid organ transplant recipients and HIV-infected patients

### **1.2. Primary purpose of the study vaccine**

Prevention of cervical, vulvar, vaginal and anal cancers and related precancerous lesions, external genital lesions, pap test abnormalities, and persistent infection caused by Human papillomavirus (HPV) types 6, 11, 16, 18, 31, 33, 45, 52, and 58 in transplant recipients and HIV-infected adults.

### **1.3. Rationale**

Human papilloma virus (HPV) is the main cause of cervical malignancies (99%) and contributes to 90% of anal cancers, 40 % of vulvar, vaginal and penile cancers and causes in lower numbers oropharyngeal and mouth cancers (1). Up to 80% of women get infected with HPV during their lives, with the highest incidence 3 to 4 years after sexual onset (2). For men the risk of infection start shortly after sexual debut and remains high for the remainder of their life and about 30% of all HPV-related cancer occurs in men. In order to induce malignancies, persistent HPV infection is needed (3). In immunocompetent persons only 10% of the infections persist >6 months.

However, in immunocompromised patients, including transplant recipients and HIV-infected patients, chronic HPV-infection is more prevailing (4). Consequently, they have an increased risk for HPV-related complications. In healthy populations, HPV vaccination is very efficacious in preventing HPV infections. Studies showed a suboptimal immunogenicity of HPV vaccination in adult transplant patients but better immunogenicity in paediatric patients and HIV-infected patients with reasonable CD4-counts (>200 cells/mm^2 or CD4% ≥15) (5-13). However, in HIV and solid organ transplant patients, only a limited number of studies has been done with the bivalent and the quadrivalent vaccine, which comprises virus like particles (VLPs) of HPV types 16 and 18 and types 6, 11, 16 and 18 respectively.

In this study, the immunogenicity of the nine-valent HPV vaccine will be investigated in HIV and solid organ transplant patients, who will be recruited in the university hospitals of Leuven.

The nine-valent vaccine that will be used in this study comprises 5 additional VLPs of oncogenic HPV types 31, 33, 45, 52 and 58 compared to the quadrivalent vaccine and consequently has an additional preventive benefit, as it increases the coverage of all cervical cancers from 70% to 90% (14). In clinical trials in women and men (16 to 26 years of age) as well as in girls and boys (9 to 15 years of age), the 9-valent vaccine was well tolerated and prevented infection and disease due HPV types included in the

vaccine (15-17). The Gardasil® was licensed in the US, Canada, Australia and Europe in respectively 2014 and 2015.

Gardasil® is currently approved for use in persons (boys and girls) as of nine years of age (Belgian SPC). Currently there are no data available for men or women above 26 years of age. Nevertheless, data are available on women 24 to 46 years of age for quadrivalent Gardasil® vaccine from the FUTURE III trial. By the end of this clinical trial, data of the V503-004 study which enrolled women between 16 and 45 years of age might be available.

#### 1.4. Summary of study design

This is a single-center, open-label study on safety, tolerability and immunogenicity of Gardasil® in 18 to 45 year-old HIV patients, in 18 to 55 year-old solid-organ transplant (SOT) patients.

This study will enrol 100 HIV patients with CD4+ count of >200cells/mm^2 and 170 SOT patients, all of whom have not yet received a prophylactic HPV vaccine. The 170 SOT patients will be equally divided over 3 different SOT patient groups, namely heart, lung and kidney transplant patients. Therefore the target is to include approximately 57 heart transplant patients, 57 lung transplant patients and 57 kidney transplant patients. Enrolment in a SOT subgroup will be stopped when 57 patients have been included unless recruitment cannot be achieved within one of the other SOT-patient population.

All enrolled subjects will receive a 3-dose regimen (Day 1, Month 2, and Month 6) of GARDASIL®. Serum samples will be collected on Day 1 and Month 7 for anti-HPV 6, 11, 16, 18, 31, 33, 45, 52, and 58 antibody determination. The time point for comparison of immune responses will be Month 7, or approximately 4 weeks after the administration of the third dose. The safety/tolerability profile of the vaccine will be evaluated in all subjects in the study. Safety information will be collected on Day 1 through 1 month following the third vaccination or for a total of approximately 7 months for each subject.

The immunogenicity and the safety data will be analyzed per group of patients. More specifically a separate analysis of HIV and SOT patients is planned, since it is expected that the immunosuppressive therapy of SOT patients might have a more profound effect on immunogenicity following vaccination.

This study will provide a comparison of immunogenicity of Gardasil® in immunocompromised patients, with historical controls (15, 18). The number of subjects to be enrolled in the study was determined based on the primary immunogenicity objective.

---

 GARDASIL® (Human Papillomavirus 9-valent Vaccine, Recombinant) is a registered trademark of Merck Sharp & Dohme Corp., a subsidiary of Merck & Co., Inc., Whitehouse Station, New Jersey, U.S.A

 GARDASIL [Quadrivalent Human Papillomavirus (Types 6, 11, 16, 18) Recombinant Vaccine] is a registered trademark of Merck & Co., Inc., Whitehouse Station, New Jersey, U.S.A. GARDASIL is also known as SILGARD in some countries. SILGARD is a trademark of Merck & Co., Inc., Whitehouse Station, New Jersey, U.S.A.

### 1.5. Dosage/Dosage Form, Route, and Dose Regimen

Subjects will receive GARDASIL®9 (HPV 9-valent vaccine [recombinant, adsorbed]) administered as a 0.5-mL intramuscular injection on Day 1, Month 2 and Month 6. The vaccine formulation is summarized in Table 1. GARDASIL®9 is available as a suspension for injection. It appears as a clear liquid with white precipitate.

**Table 1: Vaccine Formulation (0.5 mL Dose)**

HPV 6 (mcg)	HPV 11 (mcg)	HPV 16 (mcg)	HPV 18 (mcg)	HPV 31 (mcg)	HPV 33 (mcg)	HPV 45 (mcg)	HPV 52 (mcg)	HPV 58 (mcg)	Total VLP (mcg)	AAHS† (mcg)
30	40	60	40	20	20	20	20	20	270	500

† AAHS, Merck Aluminum Adjuvant (amorphous aluminum hydroxyphosphate sulfate)  
HPV, human

### 1.6. Study flow chart

Visit Windows (a) for SOT group	Consent visit	2 months after Day 1, ±4 weeks	6 months after Day 1, -1 week / +4 weeks	3 to 7 weeks after Month 6
Visit Windows (a) for HIV group	Consent visit	2 months after Day 1, -4 weeks / +2 weeks	6 months after Day 1, ±4 weeks	3 to 7 weeks after Month 6
Procedures	Visit 1 (Day 1 / Month 0)	Visit 2 (Month 2)	Visit 3 (Month 6)	Visit 4 (Month 7) (b)

Obtain informed consent form	X			
Assign screening number	X			
Review inclusion/exclusion criteria (c)	X			
Collect medical history (past year)	X			
Collect demographics	X			
Collect weight/height	X			
Update medical history (new conditions not yet recorded as medical history or adverse events (AEs))		X	X	X
Review medications and non-study vaccines (d)	X	X	X	X
Pregnancy test (urine) (e)	X	X	X	X
Collect oral/tympanic temperature (f)	X	X	X	
Assign allocation number	X			
Provide diary card	X	X	X	
Review and collect vaccination diary data		X	X	X
Blood sample for anti-HPV antibody testing (including retention serum) (10 ml blood each time) (g)	X			X
Vaccination (Intramuscular, prefer deltoid muscle of non-dominant arm; do not give into buttocks)	X	X	X	
Provide vaccination diary	X			
Review vaccination diary (h)		X	X	X
Review AE's, clinical follow up for safety (i)	X	X	X	X

(a) To calculate visit windows, assume 1 month equals 30 days and 1 week equals 7 days.

(b) Whenever possible, when a subject discontinues/withdraws prior to study completion, all applicable activities scheduled for the final study visit should be performed at the time of discontinuation except for serum collection for HPV testing.

(c) A physical examination may be performed during Visit 1 if deemed necessary by the investigator to assess eligibility criteria.

(d) See Section 3.2.4. for details of documentation times and time period restrictions for medications and non-study vaccines. If other non-study vaccines are administered at any time during the study, they should not be administered in the same limb as the study vaccine and must be appropriately documented.

(e) The serum or urine pregnancy test will be performed per the manufacturer's instructions. A pregnancy test will be performed before administration of each dose of the study vaccine and at the final Month 7 visit on all female subjects. The pregnancy test must be performed prior to serum collection for HPV testing at Day 1.

(f) If the subject has a fever (defined as an oral temperature of  $\geq 37.8^{\circ}\text{C}$ ) within the 24-hour period prior to receiving a study vaccination, the subject should not receive study vaccine, and the vaccination visit should be rescheduled until after the fever has resolved. Oral temperature will be measured prior to each vaccination

(g) Blood sample for anti-HPV measurements must be collected prior to the first study vaccination. Serum must be shipped as specified by MSD. The retention serum vial must remain at the study site until the MSD notifies the study site to ship the samples

(h) The investigator should instruct the subject to use the vaccination diary to document oral temperature in the evening after each study vaccination and daily, at the same time of day, for 4 days after each study vaccination. Additionally, injection-site and systemic adverse event(s) (AEs), concomitant

medications, and concomitant vaccinations are to be documented in the vaccination diary starting after each study vaccination for a total of 15 days, including the day of vaccination (Day 1 to Day 15).

- (i) Observe subjects for at least 15 minutes after each vaccination for immediate untoward effects. Serious adverse events (SAEs), pregnancy events, and lactation events should be reported to MSD Belgium, within 24 hours. Adverse events and SAEs will be followed for 15 days and during the whole study, respectively, after the last dose (i.e., after the third dose for subjects completing the vaccination schedule or after the last received dose in the event of the subject withdrawing).

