### **3.2 Discontinuation/Withdrawal Criteria**

#### **3.2.1. Discontinuation of Vaccination**

Discontinuation of study vaccination does not represent withdrawal from the study.

As certain data on clinical events beyond study vaccination discontinuation may be important to the study, they must be collected through the participant's last scheduled follow-up, even if the participant has discontinued study vaccination. Therefore, all participants who discontinue study vaccination prior to completion of the vaccination period, will still continue to participate in the trial.

Participants may discontinue study vaccination at any time for any reason or be dropped from the study vaccination at the discretion of the investigator should any untoward effect occur. In addition, a participant may be discontinued from study vaccination by the investigator if study vaccination is inappropriate, the trial plan is violated, or for administrative and/or other safety reasons.

A participant must be discontinued from study vaccination but continue to be monitored in the study for any of the following reasons:

- The participant requests to discontinue study vaccination.

For participants who are discontinued from study vaccination but continue to be monitored in the trial, all visits and procedures, as outlined in the trial flowchart, should be completed, except for serum collection for HPV testing at the final visit.

Participants may be allowed to begin study vaccination again if deemed medically appropriate.

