### **3.2.2. Withdrawal from the Study**

A participant must be withdrawn from the study if the participant withdraws consent from the study. If a participant withdraws from the study, they will no longer receive study vaccination or be followed at scheduled protocol visits. When a subject discontinues/withdraws from participation in the trial, all applicable activities scheduled for the final trial visit should be performed except for serum collection for HPV testing at the time of discontinuation. Any adverse events which are present at the time of discontinuation/withdrawal should be followed in accordance with the safety requirements outlined in Section 3.4.2 - Assessing and Recording Adverse Events.

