### **3.2.3. Lost to Follow-up**

If a subject fails to return to the clinic for a required study visit and/or if the site is unable to contact the subject, the following procedures are to be performed:

- The site must attempt to contact the subject and reschedule the missed visit. If the subject is contacted, the subject should be counselled on the importance of maintaining the protocol-specified visit schedule.
- The investigator or designee must make every effort to regain contact with the subject at each missed visit (e.g. phone calls and/or a certified letter to the subject's last known mailing address or locally equivalent methods). These contact attempts should be documented in the subject's medical record.
- Note: A subject is not considered lost to follow up until the last scheduled visit for the individual subject. The amount of missing data for the subject will be managed via the pre-specified data handling and analysis guidelines.

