### 3.5.4 Analysis Populations

#### 3.5.4.1 Immunogenicity Analysis Populations

##### Per Protocol Immunogenicity Population

The per-protocol immunogenicity (PPI) analysis populations will serve as the primary populations of subjects for the analysis of immune responses to each of the 9 HPV types (6, 11, 16, 18, 31, 33, 45, 52, and 58). The PPI analysis populations are HPV type-specific, i.e., each HPV type has its own PPI analysis population. To be included in a particular HPV type-specific PPI analysis population, subjects must:

- Have received all 3 vaccinations of the correct dose of GARDASIL®9 within acceptable day ranges (See Table 4).
- Have evaluable serology results at Day 1 and Month 7 based on serum samples collected within acceptable day ranges (See Table 5).
- Be seronegative to the appropriate HPV type at Day 1.
- Have no protocol deviations that could interfere with the evaluation of subject's immune response to GARDASIL®9.

To be included in the PPI analysis population for any vaccine HPV type, subjects need to be seronegative to that specific type at Day 1. The final determination of protocol deviation categories deemed as having potential to interfere with evaluation of immune response to GARDASIL®9 will be made prior to database lock and will be recorded in a separate study document.

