**Table 5: Acceptable Day Ranges for Collection of Serum Samples**

Study Visit	Target Collection Day (Relative to Day 1 † )	Day Range for Inclusion in Statistical Analysis †
Day 1	0	-14 to 0 (Relative to Day 1) ‡
Month 7	30 days after Dose 3	21 to 49 after Dose 3 §

† Day 1 refers to the date when dose 1 of study vaccine is injected. For Month 7, indicated target collection/day range is relative to date of injection of Dose 3 of study vaccine.
 
‡ Applies to both the PPI and ANSS analysis populations.
 
§ Applies to the PPI analysis population only. The day range for the ANSS analysis population is 21 to 105 days after dose 3.
 
ANSS = All type-specific naïve subjects with serology; PPI = Per-protocol immunogenicity.
		

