#### All Type-Specific Naïve Subjects with Serology Population

A supportive immunogenicity analysis will be carried out on the all type-specific naïve subjects with serology (ANSS) analysis population. The ANSS analysis populations are HPV type-specific similar to the PPI analysis populations. To be included in these sets of subjects, subjects must:

- Have received all 3 vaccinations of GARDASIL®9;
- Have evaluable serology results at Day 1 and Month 7 based on serum samples collected within acceptable day ranges (See Table 5);
- Be seronegative to the appropriate HPV type at Day 1.

To be included in the ANSS analysis population for HPV 6 and 11, subjects must be seronegative to both HPV 6 and 11 at Day 1. To be included in the ANSS analysis population for any other vaccine HPV type, subjects need to be seronegative to that specific type at Day 1.

Unlike the PPI analysis populations, ANSS analysis populations will not exclude subjects who had protocol deviations deemed as having potential to interfere with evaluation of immune response to GARDASIL®9. In addition, no day ranges on the timing of the vaccination will be applied.

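### Final HPV serum is omitted for everyone who discontinues or withdraws, including a few subjects whose sample Table 5 would accept, and no immunogenicity set includes non-completers

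*Combined protocol and SAP*

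**What the plan says.** **Serum collection.** Three places leave out the final HPV sample.

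- Section 1.6, footnote (b), for a subject who discontinues or withdraws before completing the study: "all applicable activities scheduled for the final study visit should be performed at the time of discontinuation except for serum collection for HPV testing".
- Section 3.2.1, for subjects off vaccine but still followed: "all visits and procedures, as outlined in the trial flowchart, should be completed, except for serum collection for HPV testing at the final visit". The next sentence adds: "Participants may be allowed to begin study vaccination again if deemed medically appropriate".
- Section 3.2.2, for withdrawal from the study: "all applicable activities scheduled for the final trial visit should be performed except for serum collection for HPV testing at the time of discontinuation".

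None of them makes an exception for a subject who has had all 3 doses or who is already inside the serum window.

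**Analysis sets (section 3.5.4.1).** The primary PPI set requires 3 correct doses within the Table 4 ranges, seronegativity at Day 1, and evaluable Day 1 and Month 7 serology, with the Month 7 sample 21 to 49 days after Dose 3. The supportive ANSS set relaxes the serum window ("The day range for the ANSS analysis population is 21 to 105 days after dose 3"), dose timing ("In addition, no day ranges on the timing of the vaccination will be applied") and protocol deviations. It still requires 3 doses and Month 7 serology. The seropositive (GMT) set carries the same dose and serology requirements as PPI.

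**Missing data.** Section 3.2.3 states: "The amount of missing data for the subject will be managed via the pre-specified data handling and analysis guidelines". Section 3.5 contains no rule for missing serology. The statement against imputation in 3.5.5.2 concerns safety data, and the one in 3.5.5.3 about leaving missing values out of proportions concerns descriptive summaries.

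**The concern.** There are two separate issues.

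First, the collection rule and the analysis rule do not match. Table 5 defines which post-Dose-3 samples are usable. The stopping rules omit the sample on a different criterion, namely whether the subject has discontinued or withdrawn. Where the two disagree, a primary endpoint that the plan would accept is not obtained.

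Second, the primary objective (section 2.2.1) speaks of adult HIV and transplant patients, while every seroconversion rate is conditional on completing 3 doses and giving Month 7 serum. ANSS is the only stated supportive analysis of the primary endpoint, and it shares that condition. If stopping and poor response have a common cause, such as heavier immunosuppression, the completer rate would be too favourable and nothing in the immunogenicity analysis would show it. The plan expects immunosuppressive therapy to affect response (sections 1.4 and 2.5.1) but gives no evidence on who stops.

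**Working it through.** **1. Where the serum rule and Table 5 disagree**

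| Subject | Serum under the stopping rules | Would PPI or ANSS accept the sample? |
|---|---|---|
| 3 doses, withdraws 21–49 days after Dose 3, Visit 4 serum not yet drawn | Omitted (1.6(b), 3.2.2) | Yes: ANSS, and PPI if the other criteria are met |
| 3 doses, withdraws 50–105 days after Dose 3, no Visit 4 serum | Omitted (1.6(b), 3.2.2) | ANSS only |
| Discontinues vaccination, restarts, completes 3 doses | Not stated (3.2.1) | ANSS yes; PPI only if doses fall within Table 4 |
| Stops after 1 or 2 doses | Omitted (3.2.1, or 1.6(b)/3.2.2 if withdrawn) | No: the 3-dose requirement fails |

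Only the first two rows are a definite loss of acceptable samples. The third is an ambiguity. The fourth loses nothing from the defined sets.

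**2. The plan's precision figures (section 3.5.6)**

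The 95% half-width is 1.96 × √(p(1−p)/n).

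- SOT, p = 0.80, n = 170: 6.01 points (stated ±6%).
- HIV type 18, p = 0.90, n = 80: 6.57 points (stated ±6.6%).

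Both reproduce.

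**3. Precision cost of missing serology**

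The documents give no drop-out rate, so the loss d is assumed. The sample size becomes n(1−d).

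| d | SOT n | Half-width | HIV n | Half-width |
|---|---|---|---|---|
| 5% | 162 | 6.17 | 76 | 6.74 |
| 10% | 153 | 6.34 | 72 | 6.93 |
| 20% | 136 | 6.72 | 64 | 7.35 |

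At 10% the cost is 6.34 − 6.01 = 0.33 points (SOT) and 6.93 − 6.57 = 0.36 points (HIV), which is small.

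**4. Bounds on the rate in all vaccinated seronegative subjects**

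Let p be the completer rate and d the share without Month 7 serology from any cause. If all the missing failed, the rate is p(1−d). If all responded, it is p(1−d) + d.

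| d | SOT, p = 80% | HIV type 18, p = 90% |
|---|---|---|
| 5% | 76–81% | 85.5–90.5% |
| 10% | 72–82% | 81–91% |
| 20% | 64–84% | 72–92% |

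The largest downward shift is p × d. At 5% it is 4 points (SOT) and 4.5 points (HIV), inside the stated margins. At 10% it is 8 and 9 points, outside them. It equals the stated margin at d = 6/80 = 7.5% (SOT) and d = 6.6/90 = 7.3% (HIV).

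These bounds cover missing serology from any cause. They do not measure the subjects in step 1, whose number cannot be derived from the documents.

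**The case against.** The strongest reply is that the definite loss is very small.

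- Visit 4 is scheduled 3 to 7 weeks after Month 6, that is days 21–49, which matches the Table 5 PPI window. A willing subject seen on day 25 is simply attending Visit 4 and is bled.
- A subject who comes late has not discontinued. Section 3.2.3 tells the site to reschedule, so the ANSS window stays open to them.
- What is left is formal withdrawal inside the window before the draw. Section 3.2.2 ties mandatory withdrawal to withdrawn consent, so a research sample may not be obtainable.
- A subject who has restarted is arguably no longer discontinued and returns to the flow chart.
- A subject without Dose 3 has no post-Dose-3 endpoint, so not sampling them fits the objective.
- Counting missing as failure mixes non-completion with non-response.

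Most of this stands, and it sets the limits of the point. It does not remove the mismatch, because the three passages are unconditional and the restart reading is only an inference. Nor does it answer the second issue: all three immunogenicity sets contain completers only.

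A reader might infer more than the documents support:

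- **That nobody analyses those who stop.** The ASaT safety set (3.5.4.2) includes anyone with at least 1 dose and one follow-up visit, and section 3.5.5.3 tabulates discontinuations and reasons for exclusion from PPI.
- **That sampling is forbidden.** The text leaves serum out of the activities to be done and states no prohibition.
- **That primary data are lost on any scale, or that the serum rule shifts the rate by 4 to 9 points.** Those shifts come from assumed missingness of any cause.
- **That the reported rate is too favourable.** The documents do not say who stops, and the bounds run in both directions.

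**Conclusion.** The point holds in a limited form. The serum exception takes no account of doses or timing. It therefore omits acceptable samples from a small group of 3-dose subjects who withdraw inside the Table 5 windows before Visit 4 serum, and it leaves the restart case undefined. The number affected cannot be estimated and is probably low, given the overlap with Visit 4.

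The gap in the analysis matters more. Comparing PPI with ANSS can show the effect of dose timing, deviations and late sampling, but not of completion. The size of any bias depends on an unknown proportion of missing serology. Above roughly 7% missing, the worst case exceeds the stated precision in both groups; below that it does not. Those figures assume that the plan's expected rates of 80% and 90% apply to completers. The guidelines that section 3.2.3 mentions may lie in a document not available here; the protocol and its analysis section state none for serology.

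**What to change.** (a) In section 1.6 footnote (b) and sections 3.2.1 and 3.2.2, limit the serum exception: with the subject's agreement, draw final serum from any subject who has received 3 doses and is within the Table 5 range. In 3.2.1, reconcile the restart sentence with the serum exception by stating whether a subject who resumes and completes the series has final serum taken.

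(b) Keep PPI primary. Add one supportive table per HPV type, separately for HIV and SOT, in all Day 1 seronegative subjects given at least 1 dose, counting missing Month 7 serology as not seroconverted. Label it a lower bound that mixes non-completion with non-response. State in section 3.5 that this is how missing serology is examined, so that the reference in 3.2.3 has something to point to.

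Cost: wording in three places and one additional table per type. The 10 ml draw is already a planned Month 7 procedure, and Day 1 serostatus is collected from everyone, so (b) needs no new blood. The downside is a few more assays and a less favourable supportive figure.
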